7.9.1.2.2 Integrated Continuous Glucose Monitoring (iCGM) for DS5

The 11 secondary endpoints will be evaluated in a fixed sequence of testing for adjustment of multiplicity. The results will be compared to the iCGM Special Control criteria for sensor accuracy (SG limit of 50-400 mg/dL [2.8-22.2 mmol/L]). For each of the endpoints, iCGM measurement refers to the sensor glucose value:

- % of iCGM measurements that indicate a positive glucose rate of change greater than 1 mg/dL/min when the corresponding true negative glucose rate of change is less than -2 mg/dL/min as determined by the corresponding blood glucose measurements
- % of iCGM measurements that indicate a negative glucose rate of change less than -1 mg/dL/min when the corresponding true positive glucose rate of change is greater than 2 mg/dL/min as determined by the corresponding blood glucose measurements
- Sensor values will be compared to YSI[™]* plasma glucose values during YSI[™]* FSTs. A within 20% mean agreement rate between sensor values and YSI[™]* plasma glucose values during YSI[™]* FST days will be evaluated.
- Sensor values will be compared to YSI[™]* plasma glucose values during YSI[™]* FSTs. A within 15% mean agreement rate when SG >180 mg/dL (10.0 mmol/L) between sensor values and YSI[™]* plasma glucose values during YSI[™]* FST days will be evaluated.
- Sensor values will be compared to YSI[™]* plasma glucose values during YSI[™]* FSTs. A within 40% mean agreement rate when SG >180 mg/dL (10.0 mmol/L) between sensor values and YSI[™]* plasma glucose values during YSI[™]* FST days will be evaluated.
- When iCGM values are greater than 180 mg/dL (10.0 mmol/L), the number of corresponding blood glucose values that read less than 70 mg/dL (3.9 mmol/L).

CIP330 Statistical Analysis Plan	Form
Revision [3.0] Page 19 of 25	Medtronic

- Sensor values will be compared to YSI[™]* plasma glucose values during YSI[™]* FSTs. A within 15% mean agreement rate when SG between 70 and 180 mg/dL (3.9 and 10.0 mmol/L) between sensor values and YSI[™]* plasma glucose values during YSI[™]* FST days will be evaluated.
- Sensor values will be compared to YSI[™]* plasma glucose values during YSI[™]* FSTs. A within 40% mean agreement rate when SG between 70 and 180 mg/dL (3.9 and 10.0 mmol/L) between sensor values and YSI[™]* plasma glucose values during YSI[™]* FST days will be evaluated.
- When iCGM values are less than 70 mg/dL (3.9 mmol/L), the number of corresponding blood glucose values that read above 180 mg/dL (10.0 mmol/L).
- Sensor values will be compared to YSI[™]* plasma glucose values during YSI[™]* FSTs. A within ±15 mg/dL (0.8 mmol/L) mean agreement rate when SG less than (<) 70 mg/dL (3.9 mmol/L) between sensor values and YSI[™]* plasma glucose values during YSI[™]* FST days will be evaluated.
- Sensor values will be compared to YSI[™]* plasma glucose values during YSI[™]* FSTs. A within ±40mg/dL (2.2 mmol/L) mean agreement rate when SG less than (<) 70 mg/dL (3.9 mmol/L) between sensor values and YSI[™]* plasma glucose values during YSI[™]* FST days will be evaluated.

The iCGM secondary endpoints will be independently evaluated for each of the 3 primary and 15 secondary datasets.

7.9.1.3 Agreement, ARD, Bias (Accuracy Analyses)

The following will be evaluated for each of the 3 primary and 15 secondary datasets.

The agreement, ARD (the absolute differences), and bias between the sensor and YSI[™]* relative to the YSI[™]* reference, will be calculated for each day separately. Summary statistics will include its mean, standard deviation, min, median, and max.

7.9.1.4 Descriptive Endpoints

The following descriptive endpoints will be independently evaluated for each of the 3 primary datasets.

7.9.1.4.1 Numbers of Readings in the Low and High Ranges

Every effort to safely collect data in the low and high range via the hyperglycemic and hypoglycemic challenge will be made.

7.9.1.4.2 Difference Tables Comparing Sensor and Reference Readings

Number and percentage of paired data points within 10%, 15%, 20%, 30%, 40%, 50%, 60%, 70%, 80%, 90% and 100% of the reference method (YSI[™]* for in-clinic portion and meter BG for home-use portion) will be summarized.

CIP330 Statistical Analysis Plan	Form
Revision [3.0] Page 20 of 25	Medtronic

Number and percentage of paired data within 10 mg/dL (0.6 mmol/L), 15 mg/dL (0.8 mmol/L), 20 mg/dL (1.1 mmol/L), 30 mg/dL (1.7 mmol/L), 40 mg/dL (2.2 mmol/L), 50 mg/dL (2.8 mmol/L), 60 mg/dL (3.3 mmol/L), 70 mg/dL (3.9 mmol/L), 80 mg/dL (4.4 mmol/L), 90 mg/dL (5.0 mmol/L) and 100 mg/dL (5.6 mmol/L) of the reference method (YSI[™]* for in-clinic portion and meter BG for home-use portion) will be summarized.

7.9.1.4.3 Clarke Error Grid Analysis (EGA) of Paired Sensor and YSI^{™*} and Reference Values

1) Description

Clarke Error Grid Analysis (EGA) separates paired observations into five zones of clinical significance. The presence and severity of possible treatment error based on interstitial glucose assay evaluated by the sensor defines the five zones. Zone A represents the absence of treatment error, where the evaluation method and the reference method are within 20% of one another or in which both methods indicate hypoglycemia. Zone B represents cases where the two methods disagree by more than 20%, but do not lead to treatment error. Zones C, D, and E represent increasingly large and potentially harmful discrepancies between the evaluation and the reference method. If the method under evaluation has a high percentage (greater than (>)90%) of its pairs in Zones A and B, then it is considered clinically acceptable [Clarke et al, 1987].

2) Statistical analysis

Summary statistics (N, %) for each of the zones, as well as combined Zones A and B, will be calculated.

In order to evaluate differing levels of accuracy at various YSI^{M*} defined glucose levels, the number and percentage of paired observations falling into Zones A, B, A+B, C, D, and E will be provided by YSI^{M*} glucose ranges of 40-80 mg/dL (2.2 - 4.4 mmol/L), greater than (>) 80-120 mg/dL (4.4 - 6.7 mmol/L), greater than (>) 120-240 mg/dL (6.7 - 13.3 mmol/L), and greater than (>) 240 mg/dL (13.3 mmol/L).

All analysis performed using the Clarke Error Grid comparing the paired sensor and YSI[™]* reference glucose values will be duplicated using the Continuous Error Grid [Clarke et al, 1987] and the Consensus Error Grid [Parkes et al, 2000].

7.9.1.4.4 Precision Analysis

Precision analysis will be performed for the two sensors worn by the same subject in the same location.

7.9.1.4.5 Comparison of CGM Performance to Reference under conditions leadings to Alert

CIP330 Statistical Analysis Plan		Form
Revision [3.0] Page 21 o	25	Medtronic

The alert will be triggered when the sensor BG value reaches the threshold glucose value. Predictive alerts will be evaluated by using the predicted sensor BG value based on current sensor BG and sensor BG readings within the previous 30 minutes.

In the in-clinic portion, the threshold and predictive alert analysis will be performed retrospectively with theoretical hypoglycemia threshold setting at 50 mg/dL (2.8 mmol/L), 60 mg/dL (3.3 mmol/L), 70 mg/dL (3.9 mmol/L), 80 mg/dL (4.4 mmol/L), 90 mg/dL (5.0 mmol/L) and 100 mg/dL (5.6 mmol/L) and theoretical hyperglycemia threshold setting at 180 mg/dL (10.0 mmol/L), 220 mg/dL (12.2 mmol/L), 250 mg/dL (13.9 mmol/L) and 300 mg/dL (16.7 mmol/L).

The threshold alert performance will be evaluated for in-clinic portion by true alert rate, missed alert rate and false alert rate within 15 and 30 minutes windows of the reference event. Predictive alert performance will only be evaluated for the in-clinic portion by true predictive alert rate, missed predictive alert rate and false predictive alert rate within 15 and 30 minutes windows. All reference BG values will be used, including those less than (<) 40 mg/dL (2.2 mmol/L) and greater than (>) 400 mg/dL (22.2 mmol/L).

The comparison of CGM performance to reference under conditions leading to alert will be evaluated by true alert rate, missed alert rate and false alert rate within 15 and 30 minutes window of the reference event.

Alert Rate Type	Column Label	Label Definition
Detection Rate	Hypo/Hyper Events Correctly Detected (%)	The device alarmed at the specified CGM settings within 30 minutes (or 15 minutes) before or after the reference blood glucose value (YSI™* or SMBG) goes below (for hypo) or above (for hyper) the specified CGM setting levels.
Missed Detection Rate	Hypo/Hyper Events Not Detected (%)	The device did not alarm at the specified CGM settings within 30 minutes (or 15 minutes) before or after the reference blood glucose value (YSI™* or SMBG) goes below (for hypo) or above (for hyper) the specified CGM setting levels.
True Alert	Alerts Verified by Hypo/Hyper Events (%)	There is at least one reference blood glucose value (YSI™* or SMBG) goes below (for hypo) or above (for hyper) the specified CGM setting levels within 30 minutes (or 15 minutes) before or after the sensor alarmed at the specified alert settings.

The alert rates will be defined as follows:

CIP330 Statistical Analysis Plan			Form	
	Medtronio			
Alert Rate Type	Column Label	Label Definition		
False Alert	False Alerts (%)	glucose value (YSI [™] below (for hypo) or the specified CGM 30 minutes (or 15 r after the sensor ala	There is no reference blood glucose value (YSI™* or SMBG) goes below (for hypo) or above (for hyper) the specified CGM setting levels within 30 minutes (or 15 minutes) before or after the sensor alarmed at the specified alert settings.	

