#### **10.2.1.6.4.1** Blood Glucose Monitoring During the YSI™\* FST

The frequency of blood draws for YSI™\* FST sampling is dependent on the average value of YSI-B and YSI-W probes of the previous sample, according to the following ranges:

- less than (<) 75 mg/dL (4.2 mmol/L); every 5 minutes (window of 3-8 minutes)
- greater than or equal to (≥) 75 mg/dL (4.2 mmol/L); every 15 minutes (window of 7-23 minutes)

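### The only alert-rate definitions use a window on both sides of the event and no prediction horizon is stated, so the planned predictive alert rates cannot separate advance warning from late detection.

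*SAP*

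**What the plan says.** SAP 7.9.1.4.5 plans two kinds of alert. A threshold alert is triggered when the sensor value reaches the setting. A predictive alert is formed by "using the predicted sensor BG value based on current sensor BG and sensor BG readings within the previous 30 minutes". The 30 minutes there is a look-back; how far ahead the prediction reaches is not stated.

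The predictive rates have their own sentence: "Predictive alert performance will only be evaluated for the in-clinic portion by true predictive alert rate", followed by "missed predictive alert rate and false predictive alert rate within 15 and 30 minutes windows". It gives no direction for those windows.

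One table of definitions follows, introduced by "The alert rates will be defined as follows". Its four rows all use a two-sided window:

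- Detection: "The device alarmed at the specified CGM settings within 30 minutes (or 15 minutes) before or after the reference blood glucose value" passes the setting.
- Missed detection: "The device did not alarm at the specified CGM settings within 30 minutes (or 15 minutes) before or after the reference blood glucose value" passes the setting.
- True alert and false alert: at least one, or no, reference value beyond the setting "within 30 minutes (or 15 minutes) before or after the sensor alarmed at the specified alert settings".

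Protocol 25.9.8 has the same table. No row or sentence in either document defines a predictive rate differently, requires the alert to come before the event, or asks for a lead-time summary. SAP 7.9.1.4 classes these as descriptive endpoints on the three primary datasets.

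**The concern.** A threshold alert says that glucose is beyond the setting now, so tolerance on both sides of the reference event is reasonable. A predictive alert says that glucose will get there. If it is scored with the same window, an alert that first fires 25 minutes after YSI has fallen below 70 mg/dL counts as a correct detection. An alert whose only supporting low reference value came before it counts as verified.

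Predictive rates are reported to describe advance warning. With both sides pooled, a high rate could come largely from alerts that repeat the threshold alert, and nothing else planned in the section would show it.

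**Working it through.** There is no sample size, power or stated rate to reproduce here. The check is the window arithmetic, a simple timing model, and session simulations.

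**1. Window arithmetic.** The 30-minute window spans 60 minutes, of which 30/60 = 50% lies after the event. For the 15-minute window it is 15/30 = 50%. The event is dated at the first reference sample beyond the setting, so lateness against the true crossing adds the sampling gap. Gaps are from Protocol 10.2.1.6.4.1 and 11.2.1.6.2.1, with the longest permitted gap in brackets:

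- YSI below 75 mg/dL, 5 (8) min: 30 + 5 = 35 (38) min
- YSI at or above 75 mg/dL, 15 (23) min: 30 + 15 = 45 (53) min
- SMBG above 80 mg/dL, ages 2 to 6, 30 (45) min: 30 + 30 = 60 (75) min

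This late dating already favours the device under a before-only rule, because an alert between the true crossing and the next sample counts as early.

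**2. Timing model (assumptions, not in the documents).** Let d = alert time minus reference-event time = lag − lead + N(0, SD 10) − U(0, gap). The two-sided rate is P(|d| ≤ 30). The before-only rate is P(−30 ≤ d < 0). With a 5-minute gap the mean of d is −(net lead) − 2.5, where net lead = lead − lag, and the SD is √(100 + 25/12) = 10.1.

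For net lead −10 (no look-ahead, 10-minute lag), the mean is 7.5. Two-sided: Φ((30 − 7.5)/10.1) = Φ(2.23) = 98.7%, the lower tail being negligible. Before-only: Φ(−7.5/10.1) = Φ(−0.74) = 22.9%. Simulation with 200,000 events per setting gives the same values:

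| Net lead (min) | Two-sided, 30 min | Before-only, 30 min | Difference |
|---|---|---|---|
| −15 | 95.9% | 10.7% | 85.2 |
| −10 | 98.7% | 22.9% | 75.8 |
| 0 | 99.6% | 59.4% | 40.2 |
| +5 | 98.7% | 75.8% | 22.9 |
| +10 | 95.8% | 85.0% | 10.8 |
| +20 | 77.1% | 75.8% | 1.3 |

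Net leads of −10 and +5 put the average alert 7.5 minutes after and 7.5 minutes before the reference event. The two-sided rule gives both 98.7%; the before-only rule gives 22.9% and 75.8%. Over all zero-look-ahead settings (lag 5 to 15 min, gap 5 or 15 min), the two-sided rate is 96 to 99.6% and the before-only rate 11 to 58%. At 15 minutes they are 59 to 85% and 10 to 46%.

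**3. Session simulations, setting 70 mg/dL.** These follow the planned YSI sampling through simulated 8-hour sessions, with assumed sensor lag and error.

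- Zero look-ahead, ±30 min: 96 to 97% detected against 20 to 33% with an alert beforehand in one set of runs; 98 to 100% against 22 to 50% in another.
- Look-ahead 10 min: the difference was 21 to 29 points with 8-minute lag and 9% sensor-level error, 13 to 23 points in a separate run with that lag and error, about 6 points with 5-minute lag and 5% error (100% against 94%), and 2 to 16 points in a further set.
- Look-ahead 20 min: 1 to 8 points. Look-ahead 30 min: 0 to 3 points. The further set gave 0 to 2 points for 20 to 30 min.

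The timing model is cruder and gives larger differences where net lead is zero or negative, so 0 to 29 points is an illustration and not a bound.

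**The case against.** **The table does not name predictive alerts.** The sentence just before it lists only the plain alert rates, and the predictive rates stand in an earlier sentence. A reader might infer that the sponsor has decided to score predictions with the two-sided window; the documents do not say so. The other reading is that the predictive rates have no definition. SAP 7.9.1.4.6 and Protocol 25.9.9 also state that analyses follow a cited CLSI guideline, whose content cannot be checked here. This stands as a limit on certainty, but either reading leaves the same gap.

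**The size is uncertain.** A reader might infer that the predictive rates do not measure prediction at all, or that this study's rates will be grossly inflated. The documents do not support that. The contrast at zero look-ahead shows that the measure cannot discriminate; it does not estimate this device's inflation, which nearly vanishes at a 20 to 30 minute look-ahead.

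**No size can be put on the true-alert rate.** It depends on whether repeat alarms during a long low period count, which the plan does not say. In one set of runs at a 10-minute look-ahead, 58 to 66% of all alert onsets had no earlier low reference value in the window, but 84 to 87% of first alerts did not.

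**The stakes are limited.** The endpoint carries no hypothesis, threshold or alpha, and the data can be re-scored later. That is right, but choosing the direction of the window after seeing the rates would be a post hoc choice.

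**Conclusion.** The concern holds in this form: the plan reports predictive alert rates without a definition specific to prediction and without a horizon, and the only definitions available pool alerts before and after the event. Rates built on them cannot tell prediction from late detection. That conclusion rests on the text and the window arithmetic alone.

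The size rests on assumed look-ahead, sensor lag and sensor error: about 96 to 100% scored as detected against about 20 to 50% alerted beforehand for an alert with no look-ahead, and about 0 to 29 points of inflation in the session simulations with a look-ahead of 10 to 30 minutes. The primary and secondary hypothesis tests and the study's pass/fail rule are untouched. It is a cheap improvement to a descriptive endpoint, worth making before the rates are produced.

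**What to change.** In SAP 7.9.1.4.5 and Protocol 25.9.8, keep the two-sided window for threshold alerts. For predictive alerts, state the prediction horizon and how repeat alerts are counted, and add exclusive categories.

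Event level:
- Detected in advance: a predictive alert fired in the 30 (or 15) minutes before the first reference value beyond the setting.
- Detected late: the first alert came only in the same-length window after it.
- Missed: neither.

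Alert level, each as a percentage of all predictive alerts:
- True predictive: no reference value beyond the setting in the window before the alert, and at least one in the window after it.
- Late: a reference value beyond the setting already in the window before the alert.
- False: none in either window.

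The horizon matters for reading the results: in the timing model with a 5-minute gap, a net lead of 25 minutes scores only 10.8% two-sided and 10.5% before-only at 15 minutes, because most alerts fire too early for the window.

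The two-sided predictive rates may be kept as supplementary. The cost is wording in two documents and a small programming change on data already recorded. The downside is less favourable headline predictive rates.

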7.9.1.4.6 Other Accuracy Analyses

A correlation between the sensor and YSI[™]* values will be performed. As this statistic ignores any data dependency, it will be used only as a descriptive measure of association.

A linear model, in which YSI[™]* is predicted by sensor values, using a repeated measures model, will be performed. The models solution will provide the intercept and slope, while adjusting for dependence in the data within day. An intercept of 0, along with a slope of 1, would indicate the absence of bias in predicting YSI[™]* from sensor readings. The residuals of the model will be inspected to determine if transformation of either variable is required.

Bland-Altman plots, with 95% confidence interval (CI), will be provided. The paired differences between the sensor and YSI[™]* rating will be plotted against the X-axis reference of mean YSI[™]* and sensor values.

Descriptive subgroup analysis of DS5 sensor performance (20% mean agreement rate (±20 mg/dL [1.1 mmol/L] when SG less than (<) 80 mg/dL [4.4 mmol/L]) will be performed in the following cohorts:

- Diabetes cohorts based on insulin requirement:
 - Type 1 insulin requiring
 - Type 2 insulin requiring
 - Type 2 non-insulin requiring
- Diabetes cohorts based on Centers for Disease Control and Prevention (CDC) classification for younger than 20 years old:

A description of the following 4 groups will be performed:

- Underweight subjects (less than (<) 5th percentile)
- Normal weight subjects (5th percentile to less than (<) 85th percentile)
- Overweight (85th to less than (<) the 95th percentile)
- Obese subjects (greater than or equal to (≥) the 95^{th} percentile)

CIP330 Statistical Analysis Plan		Form
Revision [3.0]	Page 23 of 25	Medtronic

• Diabetes cohorts based on BMI according to WHO criteria [World Health Organization, 2011] for subjects equal to or greater than 20 years old:

A description of the following 5 groups will be performed:

- Underweight subjects (BMI less than (<)18.5 kg/m²)
- Normal weight subjects (BMI 18.5 to 24.99 kg/m²)
- Overweight and obese subjects (BMI 25.00 to 40 kg/m²)
 - Overweight subjects (BMI 25.00 to 29.99 kg/m²)
 - Obese subjects (BMI 30.00 to 39.99 kg/m²)
- Morbidly obese subjects (BMI greater than or equal to (≥)40 kg/m²)
- Diabetes cohorts based on prior real-time CGM experience (by self-report)
 - o CGM naïve
 - CGM experienced
- Diabetes cohorts based on prior pump experience (by self-report)
 - o Pump naïve
 - o Pump experienced
- Diabetes cohorts based on HbA1c:
 - Baseline HbA1c (by certified National Glycohemoglobin Standardization Program, NGSP, method) will be collected:
 - A description of the following 3 groups will be performed: HbA1c less than (<) 7%, HbA1c 7-9%, HbA1c greater than (>) 9%
 - o Quartile comparison (lowest to the highest) based on HbA1c
- Diabetes cohort based on exercise activity:
 - Per Investigator's discretion, subjects may participate in the exercise in order to obtain low glucose values.

All analyses follow the definitions provided in: Performance Metrics for Continuous Interstitial Glucose Monitoring: Approved Guideline, CLSI POCT05-A [Klonoff et al. 2008].

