5.2 Study Design: Subjects 2-13 years

It is expected that subjects 7 - 13 years will complete 2 days of YSI[™]* FST with the sensors and subjects 2 - 6 years will complete 2 days of SMBG FST with the sensors. Subjects ages 2 – 6 years will only do SMBG during their FST.

Subjects will wear sensors in the following configurations and follow the FST schedule:

Subjects 7 - 13 years

- Sensor Location
 - Arm/Arm/Buttock
 - Buttock/Buttock/Arm
- o FST Schedule

Revision [3.0]

• 2 x 6 hours FST

Subjects 2 - 6 years

- o Sensor Location
 - Arm/Buttock
 - Subjects 2-6 years old may have their parent, guardian, or legally authorized representative choose the area for their sensor placement
- o FST Schedule
 - 2 x 4 hours FST
 - SMBG only

FST Timing for 7-13 years old:

Group	Sensor Wear Day	Timing of FST from Sensor Insertion T=0
A1	Day 1, 7	2-8 hours (+2), 146-152 hours (±6)
A2	Day 1, 7	20- 26 hours (±2), 164-170 hours (-6, +2)
B1	Day 2, 5	26-32 hours (±2), 116-122 hours (±6)
B2	Day 2, 5	44-50 hours (±2), 98-104 hours (±6)
C1	Day 3, 5	50-56 hours (±6), 116-122 hours (±6)
C2	Day 3, 5	68-74 hours (±6), 98-104 hours (±6)
D1	Day 4, 6	74 -80 hours (±6), 140-146 hours (±6)
D2	Day 4, 6	92-98 hours (±6), 122-128 hours (±6)

FST Timing for 2-6 years old:

Group	Sensor Wear Day	Timing of FST from Sensor Insertion T=0
A1	Day 1, 7	2-6 hours (+2), 148-152 hours (±6)
A2	Day 1, 7	20- 24 hours (±2), 166-170 hours (-6, +2)
B1	Day 2, 5	26-30 hours (±2), 118-122 hours (±6)
B2	Day 2, 5	44-48 hours (±2), 100-104 hours (±6)
C1	Day 3, 5	50-54 hours (±6), 118-122 hours (±6)
C2	Day 3, 5	68-72 hours (±6), 100-104 hours (±6)
D1	Day 4, 6	74 -78 hours (±6), 142-146 hours (±6)
D2	Day 4, 6	92-96 hours (±6), 124-128 hours (±6)

Sensors worn in the same insertion site location may be inserted on same side or opposite sides. Sensors may be inserted with the assistance of a caretaker.

CIP330 Statistical Analysis Plan	Form
Revision [3.0] Page 10 of 25	Medtronic

Subjects will continue with their current diabetes regimen independent of the study devices. Subjects will be instructed by the investigational center that they are not to use the study devices (except for the study meter) for the management of their diabetes.

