Subjects will wear the devices up to 7-day training period, followed by a 7-day study period. Investigational center staff will ensure 176-188 hours of sensor wear (sensors may be removed at that time or after that time to ensure that the devices are not removed pre-maturely). In the event early sensor removal occurs during the training period, the subject can continue to study period based on PI discretion.

During the YSI[™]* FST, IV blood samples will be drawn every 5-15 minutes and analyzed using the YSI[™]* for subjects 7-13 years. For subjects aged 2 – 6 years, the frequency of blood draws with SMBG is every 5 – 30 minutes.

The YSI^{™*} FST will be approximately 6 hours during the in-clinic visit for subjects 7- 13 years. The SMBG FST will be approximately 4 hours during the in-clinic visit for subjects 2-6 years. For details on maximum amount of blood drawn refer to Synopsis and Stopping Rules for Subjects for FST (section 20.1.1 in the protocol).

For device troubleshooting and device complaints (See Section 24 in the protocol):

- **US only**: Subjects and/or Sites are to call the 24-Hour Technical Support (TS)
- China only: Subjects are to call Investigational Center staff

Hypoglycemic and Hyperglycemic Challenges

Subjects 2 - 13 years:

During the day of FST, subjects will not participate in hypoglycemic and hyperglycemic challenges.

6. Determination of Sample Size

A total of up to 376 previously-diagnosed type 1 or type 2 diabetes subjects in the U.S. and China will be enrolled in order to have 260 subjects complete the study.

Up to 22 investigational centers in the US and China will be used during the study.

US:

A total of up to 300 previously-diagnosed type 1 or type 2 diabetes subjects in the U.S. will be enrolled in order to have 200 subjects complete study.

Up to 17 investigational centers in the US will be used during the study.

CIP330 Statistical Analysis Plan Form Revision [3.0] Page 11 of 25 Medtronic

Number of subjects to complete study:

- N= 100 subjects 18-80 years old
- N= 100 subjects 2-17 years old

The US investigational centers will be encouraged to include subjects of different ethnicities including Hispanic, Native American, Asian, and African-American.

China:

A total of up to 76 previously-diagnosed type 1 or type 2 diabetes subjects in China will be enrolled in order to have 60 subjects complete study.

Up to 5 investigational centers in China will be used during the study.

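### The descriptive regression of YSI on sensor values allows for correlation within day only, although one sensor is normally read on two or four days; standard errors for its slope and intercept could be too small

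*SAP*

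**What the plan says.** SAP 7.9.1.4.6 (repeated in Protocol 25.9.9) describes a linear model in which YSI is predicted from the sensor value, "using a repeated measures model, will be performed". On correlation it says only: "The models solution will provide the intercept and slope, while adjusting for dependence in the data within day". The estimates are then interpreted: "An intercept of 0, along with a slope of 1, would indicate the absence of bias in predicting" YSI from the sensor. The repeated unit, the covariance structure and any random effects are not stated. No interval, test or threshold is given for the slope or intercept. The only interval named in the section belongs to another display: "Bland-Altman plots, with 95% confidence interval (CI), will be provided".

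The model is one of the descriptive analyses: "The following descriptive endpoints will be independently evaluated for each of the 3 primary datasets". All three of those datasets use 0 calibration (SAP 7.9).

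On the design, SAP 5.1 gives ages 14-80 four 8-hour YSI sessions on four wear days, for example days 1, 3, 4 and 7. SAP 5.2 gives ages 7-13 two 6-hour sessions, and subjects aged 2-6 "will only do SMBG during their FST". Protocol 25.8.1 assigns one primary sensor per subject per location. Protocol 13.1.2 has remaining sessions completed on new sensors after a primary sensor dislodges.

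**The concern.** Each location-specific dataset normally holds one sensor per subject, read in two or four sessions. A sensor that reads high on day 1 may well read high on day 7, and with 0 calibration no fingerstick re-anchors it in between. A model that allows for correlation only within a day counts each sensor-day as a new independent unit, so 100 adults with four sessions each become 400 units.

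What is at stake is the stated precision of the model meant to describe bias. Estimates will not land exactly on 0 and 1, so a reader needs some measure of uncertainty to judge them. If that measure is too small, chance departures look like bias, or the bias estimate looks firmer than it is.

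**Working it through.** The documents give no standard error, interval or variance component for this regression, so there is no planned figure to reproduce. The variance components below are assumptions.

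**Inputs from the documents.** Sessions per sensor: K = 4 (ages 14-80), K = 2 (ages 7-13), none for ages 2-6. Pairs per session: at glucose of 75 mg/dL or above, sampling is "every 15 minutes (window of 7-23 minutes"), so 8 hours gives 8 × 60 / 15 + 1 = 33. Adult US dataset (SAP section 6): "N= 100 subjects 18-80 years old".

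**Closed form, for a mean-bias (level) term only.** With r the correlation between a sensor's day-level errors,

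true SE / within-day-only SE = √(1 + (K − 1)r), and coverage = 2Φ(1.96 / ratio) − 1.

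| K | r | SE ratio | Interval width, % of correct | Coverage of nominal 95% |
|---|---|---|---|---|
| 4 | 0.1 | √1.3 = 1.14 | 88 | 91% |
| 4 | 0.3 | √1.9 = 1.38 | 73 | 85% |
| 4 | 0.5 | √2.5 = 1.58 | 63 | 79% |
| 2 | 0.1 | √1.1 = 1.05 | 95 | 94% |
| 2 | 0.3 | √1.3 = 1.14 | 88 | 91% |
| 2 | 0.5 | √1.5 = 1.22 | 82 | 89% |

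**Simulation of the regression, four days.** 600 runs of 100 sensors × 4 days × 33 pairs. Assumed: day offset SD 8 mg/dL, residual SD 15 mg/dL, sensor offset SD 0, 6 or 10 mg/dL, sensor gain SD 0, 5% or 10%. The error is placed on the outcome, so the true intercept is 0 and the true slope is 1. The fit is generalised least squares with a random day intercept. Robust standard errors are clustered either by sensor-day or by subject. Each cell gives coverage under a challenge-type glucose pattern / an observation-only pattern.

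| Sensor offset SD, gain SD | By day: intercept | By day: slope | By subject: intercept | By subject: slope |
|---|---|---|---|---|
| 0, 0 | 96.0 / 94.5% | 95.2 / 95.7% | 95.5 / 94.0% | 94.8 / 95.0% |
| 6, 0 | 89.0 / 90.5% | 95.0 / 93.7% | 93.5 / 95.3% | 94.0 / 94.3% |
| 10, 0 | 81.7 / 86.0% | 96.0 / 93.5% | 93.5 / 94.7% | 94.3 / 94.8% |
| 0, 5% | 95.3 / 93.2% | 84.7 / 83.7% | 94.5 / 93.7% | 95.5 / 94.2% |
| 0, 10% | 95.0 / 93.5% | 76.5 / 76.0% | 94.7 / 93.7% | 94.8 / 95.8% |
| 6, 10% | 90.0 / 91.8% | 77.2 / 74.3% | 93.8 / 94.8% | 95.2 / 94.2% |

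A persistent offset damages the intercept and leaves the slope about right. A persistent gain error damages the slope and leaves the intercept about right. Coverage of the affected term runs from 74.3% to 91.8%. Subject clustering restores 93.5-95.8% throughout.

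**Two days.** A simulation with persistent sensor error and two sessions gave about 91-92% with day-only standard errors, consistent with the K = 2 rows of the closed form.

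**Random intercept as an alternative.** With percentage sensor error (sensor SD 5-8%, day SD 3-5%, pair SD 8%; 100 × 4 × 32; glucose distribution assumed), a subject random intercept with day nested in it gave a true slope SD 1.9-2.8 times the model-based SE and coverage of about 51-68%. Subject-clustered standard errors were about right there (ratio 0.94-1.03). A random intercept alone therefore may not correct the slope.

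**The case against.** Four points stand against a stronger claim.

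- **No interval is promised.** A reader might infer that planned slope and intercept intervals are wrong. The text promises only the two estimates. The criticism concerns any standard error or interval reported from the model. It still matters, because the same section limits the simple correlation to descriptive use for ignoring dependence and then offers this model as the one that adjusts for it.
- **It is descriptive.** A reader might infer that the accuracy claim is affected. It is not: study success rests on the primary agreement rate, tested by GEE with its own correlation structure (SAP 7.9.1.1), and the regression feeds no hypothesis or pass/fail rule.
- **The wording may be loose.** A repeated measures model could have the subject as the repeated unit with day nested in it, and the sentence does not exclude that. But within day is the only level it names, and that level is too low for this design. If a subject term is intended, the SAP should say so, since its section 8 provides for independent programming of outputs.
- **The size is assumed, and four days is the worst case.** A reader might take 1.38 or 1.58 as the understatement for this regression. Those factors are for a mean with four days. Two of the three primary datasets are paediatric, where only ages 14-17 have four sessions.

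**Conclusion.** The point holds in a conditional form. The stated level of adjustment is too low for a design that normally reads one sensor on two or four days. If sensors carry a persistent offset or gain error, standard errors or intervals for the intercept or slope respectively would be too small. Nominal 95% coverage then falls to roughly 75-92% with four days and about 91-92% with two. If there is no sensor-level effect, coverage stays near 95%.

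These figures rest on assumed variance components, and the documents give none. The direction follows from the design; the amount does not. The paediatric datasets mix ages with four, two and no YSI sessions in proportions the documents do not fix. This is a minor, low-cost improvement to a descriptive analysis.

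**What to change.** In SAP 7.9.1.4.6 and Protocol 25.9.9, change the wording to: *adjusting for dependence within subject (sensor) and within day*. Keep the planned within-day correlation, use robust standard errors clustered by subject, and report the slope and intercept with the resulting intervals. If random effects are used instead, include a sensor-level random slope as well as a random intercept, with day nested within sensor.

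The cost is a short change to the model statement and somewhat wider intervals where sensors do differ persistently. No new data are needed, and the primary analysis does not change.
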